Name: v2_Lay Summary

View: v2_Justification, Objective, & Research Design

Justification, Objective, & Research Design

If you uploaded a separate research protocol document in the 'Research Protocol' page, cite the applicable section and page numbers from that document in the answer boxes below.

- 1 * Describe the purpose, specific aims, or objectives of this research. State the hypothesis to be tested:

In this study, 371 individuals with pre-dialysis CKD were consented to achieve a cohort of 350 that proceeded to study procedures with the following objectives:

1) Assess the Tolerability and Efficacy of a Commonly-used Medical Alert Accessory Designed to Increase Recognition of Chronic Kidney Disease (CKD) in a Pilot Sample of Participants from the SAFE KIDNEY CARE COHORT

The first 108 subjects of the Safe Kidney Care cohort (Phase I) were provided a medical alert accessory (choice of bracelet or necklace, stainless steel or sterling silver). Regular contacts were made with Phase I participants to monitor tolerance of medical alert accessory along with the use of a supplemental informational website on best safe practices for patients with CKD, and to measure the frequency of newly-developed Patient Safety Indicators specific to CKD (CKD-PSI).

2) Validate Established CKD-PSIs in a Cohort of Individuals with CKD Tracked Longitudinally

After enrollment in Phase I has concluded, an additional 242 volunteers from the target population were enrolled into the Safe Kidney Care cohort (Phase II) for a total of 350 participants tracked longitudinally to detect the incidence of established CKD-PSIs, assess their measurability, and exam the relationship between the occurrence of these safety events and adverse renal outcomes.

- 2 * Discuss the research design including but not limited to such issues as: probability of group assignment, potential for subject to be randomized to placebo group, use of control subjects, etc.:

Study design: Observational cohort study. Study population: Persons with Stage III – V, pre-dialysis CKD enrolled from a single center (n = 350). The first 108 participants (Phase I) were provided a medical alert accessory (choice of bracelet or necklace).

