Study Measurements: Participants in both Phase I and II underwent baseline and annual in-center visits for medical history and medication review, anthropometric measures, measurement of renal function (serum Cr for estimation of GFR); other laboratory measures, measures of physical function and health literacy, and other questionnaires. Additionally, they had a follow-up telephone call between annual visits to review medications, update contact information, assess for medical events and hospitalizations. Phase I participants also had an assessment of medical alert accessory acceptance and tolerance. The expected duration of study allows up to 4 annual clinic visits and up to 4 mid-year telephone follow-up visits through June 30, 2016. Beginning, July 1, 2016, annual clinic visits stop and will be replaced with just the annual telephone visit up to December 2021. The mid-year telephone follow-up will stop.

Primary outcomes: CKD-PSIs including medication errors (such as NSAIDs, improperly dosed meds), toxic exposures (such as contrast agents), and medical events (such as hyperkalemia or hypoglycemia); Secondary outcomes: including changing renal function, hospitalization, ESRD, and death. Phase I participants were followed for acceptance and tolerance of medical alert accessory.

- 3 * Describe the relevant prior experience and gaps in current knowledge. Describe any relevant preliminary data:
Refer to Protocol item 5. BACKGROUND

- 4 * Provide the scientific or scholarly background, rationale, and significance of the research and how it will add to existing knowledge:

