

2 If available, upload your applicable literature search:

Name	Created	Modified Date
There are no items to display		

3 * Provide a list of 3 keywords or search terms (1 per line) relevant to your research that would help potential participants find your study using search engines:

Keyword 1: patient safety

Keyword 2: chronic kidney disease

Keyword 3: medical errors

ID: VIEW4E02805A7E400
Name: v2_Supporting Literature

View: v2_Study Procedures

Study Procedures

If you uploaded a separate research protocol document in the 'Research Protocol' page, cite the applicable section and page numbers from that document in the answer boxes below. (If this study is a collaborative UM/VA study please list each procedure that is being conducted and the locations where it is being conducted.)

1 * Describe all procedures being performed for research purposes only (these procedures would not be done if individuals were not in the study) and when they are performed, including procedures being performed to monitor subjects for safety or to minimize risks:

Beginning July 1, 2016, Mod 11 replaces the annual clinic visit with a 10-15 minute telephone call and eliminates the mid-year telephone follow-up visit. In addition, study procedures were also drastically reduced and are now restricted to the following data collection at the annual telephone visit:

- Self-reported safety events leading to hospitalizations/ER visits,
- Death and cause of death,
- Onset of end-stage renal disease requiring renal replacement therapy (dialysis and/or kidney transplant), and
- Updated contact information

Mod 12 adds the Clarke Hypoglycemia Index_Questionnaire_6.20.2016 to the above data collection to measure frequency and severity of hypoglycemic episodes.

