As outlined previously, events will be ascertained from several sources including study visits, medical history review, medication review, and retrieval of hospitalization records. The source of events will be accordingly labeled. Poisson regression will be employed to determine key measured factors which predict the incidence of patient safety events. For this analysis, there will be no predetermined primary exposure to be tested in the regression analysis; however, a key analysis will be the relationship between entry GFR and incidence of CKD-PSIs. Other exposures of interest will be examined. The Poisson regression will assume the number of events for each subject follows a Poisson distribution with mean being a product of the length of the follow-up period and the rate of events, where the logarithm of the expected rate of events (per patient-month), is the linear combination of the covariates. We will check whether data display any over-dispersion and may use negative-binomial regression model if over-dispersion is present.

The data will also be structured such that it is possible to explore the relationship between the incidence of CKD-PSIs and key renal endpoints (secondary outcomes). The key adverse secondary outcomes measures to be examined will be 1) hospitalization and, 2) rate of change in renal function, as measured by estimated GFR. For hospitalization, the primary measure will be incidence of unique hospitalizations over the observed patient-months in each group. Comparisons groups will be the patient-months labeled by the prior incidence or absence of CKD-PSIs in a given patient. While an individual without any CKD-PSI during study observation has a hospitalization, that event occurs in the non-PSI group, another individual with at least one CKD-PSI in the study period who has two hospitalizations – one before and the other after the incidence of the CKD-PSI – will contribute two hospitalization events to the data set. The first will be assigned to the non-CKD-PSI group and corresponding to the period from entry to the occurrence of the first CKD-PSI, the second event will be assigned to CKD-PSI group and corresponding to the period from the occurrence of the first CKD-PSI to last follow up time or the end of the study.

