Generalized estimating equations (GEE) with log link function will be employed for examination of the relationship between incidence of CKD-PSIs and hospitalization. GEE will allow for joint modeling of the repeated measures and the incorporation of such a time-varying covariate based in the detection of a CKD-PSI. The effect of ever experiencing CKD-PSI during the study period on the frequency of hospitalization will be displayed by the rate ratio and its 95% confidence interval of hospitalization in PSI group versus non-PSI group.

Estimated GFR will be determined at baseline and at all annual follow-up visits. Since enrollment will be planned to ensure at least one follow-up visit per individual, it will be possible to generate slope estimates for change in renal function in all study participants. Measurement of serum creatinine will be done at a single laboratory to minimize variation in calibration across laboratories, and GFR will be estimated with the modified MDRD equation. Proper transformation will be performed as needed if the distribution of GFR values is skewed. Random effects models will be used to compare change in GFR between those with and without a CKD-PSI. To employ random effects models as a means to compare change in renal function between those participants with and without the incidence of a CKD-PSI and adjust for multiple covariates, the following assumptions will be made:

Each individual will have a separate slope β_i , with an independent intercept α_i , and an error term ϵ_i with mean 0 and a Normal distribution. The residual variance of each slope is assumed to be the same across all individual slopes and the distribution of β_i for participant time assigned to each group is assumed to be a Normal distribution with a mean of b_1 or b_2 corresponding to the two groups (without or with the bracelet/necklace). Similarly, the distribution of individual intercept α_i is assumed to be a Normal distribution with an equal variance across all individuals, and a mean of a_1 or a_2 corresponding to the two groups.

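### An admission can itself start CKD-PSI time, so the secondary hospitalization rate ratio can exceed 1 without any CKD-PSI effect if admission risk varies between participants or rises after discharge

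*Combined protocol and SAP*

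**What the plan says.** All of this is in Sample Size and Data Analysis, item 2 (protocol section 9.I.3), unless stated.

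- **Where CKD-PSIs come from:** "events will be ascertained from several sources including study visits, medical history review, medication review, and retrieval of hospitalization records". The plan adds: "The source of events will be accordingly labeled".
- **Dating:** each event is recorded at the time it occurs, so a CKD-PSI arising in hospital is dated within the admission.
- **Comparison groups:** patient-months are divided by whether a CKD-PSI has already occurred. Non-CKD-PSI time runs from entry. For a participant with one hospitalization before and one after the first CKD-PSI, "the second event will be assigned to CKD-PSI group and corresponding to the period from the occurrence of the first CKD-PSI".
- **Model:** a GEE with log link, chosen partly for the "incorporation of such a time-varying covariate based in the detection of a CKD-PSI". The result is a rate ratio with a 95% confidence interval, described as the effect of ever experiencing a CKD-PSI.
- **Later follow-up:** from July 2016 the annual call collects "Self-reported safety events leading to hospitalizations/ER visits" (Lay Summary; Study Procedures, item 1).

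The hospitalization analysis names no source restriction, lag, post-discharge washout or prior-admission term. It does not say which group receives the admission in which the first CKD-PSI is found, and it does not name the working correlation.

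**The concern.** The outcome feeds the exposure. The CKD-PSIs named in the research design include contrast exposure, hyperkalemia and hypoglycemia, all of which can arise or be documented during an admission. When that happens, the CKD-PSI clock starts at an admission, while the comparison clock starts at study entry.

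Two ordinary features of hospital data then push the ratio up. If risk is raised for a time after discharge, part of that raised period falls at the start of CKD-PSI time. If some participants are admitted more often than others, they switch groups sooner and take their higher rate with them. Neither requires a CKD-PSI to cause anything.

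One stated aim is to determine how far CKD-PSIs contribute to adverse outcomes, and hospitalization is the first key secondary outcome listed. A ratio above 1 from this mechanism would be read as support for the study's overall hypothesis.

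**Working it through.** The plan gives no expected ratio, event count or power for this comparison, so there is no figure of its own to reproduce. The check is what the ratio would be if the true effect were 1.

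**Inputs from the documents.** 350 participants (108 + 242). Visits to mid-2016: "The expected duration of study allows up to 4 annual clinic visits and up to 4 mid-year telephone follow-up visits through June 30, 2016". A medication error in 30% of participants per year, which as a rate is −ln(1 − 0.30) = 0.36 per person-year; the source split is not given.

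**Assumed inputs.** Admission rate λ = 0.4 per year over T = 4 years (0.5 per year over 24 to 48 months in a second set of runs). Share q of admissions showing a CKD-PSI. Outside-hospital CKD-PSI rate o. Admission rate multiplied by k for 3 months after an admission. Gamma variance v between participants in admission rate.

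**1. Closed form, k = 1, index admission in the non-CKD-PSI period.** The proportion not yet switched at time t is S(t) = exp(−ot)·(1 + vqλt)^(−1/v). Non-CKD-PSI time is T0 = ∫S(t)dt, and its admissions are E0 = ∫λ·S(t)/(1 + vqλt)dt, both from 0 to T. Total time is 4 years and total admissions 0.4 × 4 = 1.6 per participant.

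- o = 0.15, q = 0.3, v = 0.5: T0 = 2.478, E0 = 0.905, so the non-CKD-PSI rate is 0.365. The CKD-PSI rate is (1.6 − 0.905)/(4 − 2.478) = 0.457. Ratio 1.25.
- o = 0.36, other inputs the same: T0 = 1.796, E0 = 0.665, rates 0.370 and 0.424. Ratio 1.15.
- v = 0: both rates equal λ. Ratio 1.00.

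**2. Simulation with a true effect of 1.** Group split as in 9.I.3, index admission in the non-CKD-PSI period, independence working correlation, λ = 0.4, 4 years. Ranges are repeat runs.

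| o per year | q | k | v | Rate ratio | Trials of 350 with 95% CI excluding 1 |
|---|---|---|---|---|---|
| 0.70 | 10% | 2 | 0.5 | 1.06 | 6% |
| 0.36 | 10% | 2 | 0.25 | 1.07 | 12% |
| 0.36 | 10% | 2 | 0.5 | 1.13 | 22% |
| 0.36 | 20% | 2 | 0.5 | 1.20 | 42% |
| 0.15 | 30% | 1 | 0.5 | 1.24–1.26 | 57–70% |
| 0.15 | 20% | 2 | 0.5 | 1.31–1.35 | 78–80% |
| 0.15 | 30% | 3 | 0.5 | 1.59–1.64 | over 99% |
| 0.15 | 30% | 3 | 0 | 1.15–1.16 | 33% |
| 0.15 | 30% | 1 | 0 | 1.00 | 3% |

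**3. Working correlation.** In the second set of runs (o = 0.36, q = 30%, k = 3, v = 0.5), changing from independence to exchangeable lowered the ratio from 1.54 to 1.31, and the share of trials with the interval wholly above 1 from 97% to 67%.

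**4. Where the index admission goes.** With k = 1 and v = 0, counting it in the CKD-PSI group gives a ratio of (1 + q·T0/T1)/(1 − q), where T1 is CKD-PSI time. This is never below 1/(1 − q): 1.18 at q = 0.15 and 1.43 at q = 0.30. With λ = 0.5, o = 0.36, q = 0.30 and 3 years, T0 = 1.536 and T1 = 1.464, so the ratio is (1 + 0.30 × 1.536/1.464)/0.70 = 1.88. Simulated trials of 350 gave 1.87.

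**5. Alternatives, true effect 1.** Letting only outside-hospital CKD-PSIs start the group gave 0.98 to 1.05 when those events were unrelated to admission-proneness, but 1.34 to 1.73 when they were related to it. Comparing readmissions after a first admission, by whether that admission's records show a CKD-PSI, gave 0.92 to 1.02 in every scenario, including the related ones.

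**The case against.** The plan's split is careful in one respect: hospitalizations before the first CKD-PSI stay in the non-CKD-PSI group. The comparison is secondary and exploratory, the primary composite incidence is untouched, and the source of every event is recorded, so a split by source could be produced at any time. All of this stands, and it limits the weight of the point. It does not remove it, because no such split is planned.

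The size is also open to challenge, and rightly. The largest ratios need few CKD-PSIs outside hospital and an independence working correlation. The plan reports 14.8% of participants per year with hypoglycemia and 30% with a medication error, and expects the composite to be substantial; frequent outside events dilute the bias. The item excerpts a fuller protocol, and the endorsed CKD-PSI list, which governs the in-hospital share, is not in what is available.

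Three stronger readings are tempting, and the documents do not support them:

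- **That the ratio must exceed 1 under the null.** It is 1.00 with a constant common admission rate and the index admission in the non-CKD-PSI period.
- **That adjusting for entry GFR would leave the bias in place.** No calculation here includes GFR, so nothing is claimed either way.
- **That restricting to outside-hospital CKD-PSIs gives a clean ratio.** Step 5 shows that this fails if admission-prone participants also have more CKD-PSIs outside hospital. Events reported by call from July 2016 are, moreover, themselves described as leading to hospitalization or an ER visit.

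**Conclusion.** The point holds as a conditional bias. As written, an admission can start CKD-PSI time. If admission risk rises after discharge or differs between participants, the ratio exceeds 1 with no CKD-PSI effect. In a cohort spanning Stage III to V, analysed with a method chosen for repeated measures, equal and constant admission risk for everyone is unlikely, though the documents do not quantify this.

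The size rests on assumptions: about 1.1 to 1.2 with outside-hospital CKD-PSIs at 0.36 per year, 10% to 20% of admissions showing one, doubled risk for 3 months and variance 0.5; about 1.2 to 1.6 at 0.15 per year with 20% to 30%, multipliers of 1 to 3 and the same variance. An exchangeable working correlation reduces these figures. Counting the index admission in the CKD-PSI group, which the text leaves open, would add a further and often larger excess. Only the hospitalization ratio is affected, not the incidence of CKD-PSIs.

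**What to change.** In 9.I.3, use the source label already recorded:

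1. State that the admission in which the first CKD-PSI arises or is found stays in the non-CKD-PSI period.
2. Beside the all-source ratio, report it split by whether the first CKD-PSI was found outside an admission, or in an admission's records or linked to one. Count calls from July 2016 that report events leading to hospitalization or an ER visit as admission-linked. Do not present the outside-only ratio as free of bias.
3. For CKD-PSIs found in admissions, compare readmissions in the 12 months after discharge from the first admission, by whether that admission's records show a CKD-PSI, so that both sides start at a discharge.
4. Do not interpret the all-source ratio alone as the contribution of CKD-PSIs to hospitalization.

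Cost: plan wording, a recode of existing data and a little more analysis; no new collection. Intervals will be wider. Item 1 gives up any index admission that a CKD-PSI truly caused. Item 3 equalizes the starting point but not the severity of the first admission, so it remains an observational comparison.

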In this study, volunteers were enrolled from the population with pre-dialysis CKD for the purpose of observing the frequency of CKD-PSI in the target population detected over time. The participants were assessed every 6 months via 1 annual clinic visit and 1 mid-year brief telephone follow-up for events that relate to CKD-PSI. The first 100 participants (Phase I) were provided with a standard medical alert accessory (bracelet or necklace) which is commonly used to alert doctors and other providers of a patient's disease state. In this case the medical alert accessory stated "Decreased Kidney Function. For My Care, Please Visit www.safekidneycare.org" Participants were asked to log onto a website using a unique 4-digit ID assigned by the PI to track their use of the website and to further improve the website. Since all information on the website was available to the public, participants are not required to use the ID to access the content of the website. The website did not collect or store patient health

information, except for the IP address which provides limited information on the location of the computer used to access the website (city, state, zip, and area code).

The volunteers in Phase I were tracked over time as to whether they accept and tolerated the medical alert bracelet/necklace and for their incidence of CKD-PSI. Enrollment continued after Phase I into Phase II (n = 250) with Phase II participants tracked on an identical study schedule for detection of CKD-PSI. All study procedures are the same for Phase II except for the medical alert accessory. The overall goal of this study will be to determine the frequency of CKD-PSI in the target population, the acceptability of an alert device (Phase I only) intended to increase the recognition of CKD, and the contribution of CKD-PSI to the high incidence of adverse outcomes in CKD.

Due to limited funding, beginning July 1, 2016, annual clinic visits stopped and study procedures were reduced to one, brief annual telephone follow-up to continue capture

- Self-reported safety events leading to hospitalizations/ER visits,
- Death and cause of death,
- Onset of end-stage renal disease requiring renal replacement therapy (dialysis and/or kidney transplant), and
- Updated contact information
- Frequency and severity of hypoglycemic episodes for participants with diabetes

Annual data collection of above-noted elements will continue for an additional 5 years through December 2021.

ID: VIEW4E02805CF7000

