300 \pm 3.3% \pm 4.7% \pm 5.3% \pm 5.7%

- 2 * Provide the plan for data analysis. Include in the description the types of comparisons that are planned (e.g., comparison of means, comparison of proportions, regressions, analysis of variance, etc.), which is the primary comparison/analysis, and how the analyses proposed will relate to the primary purposes of the study:

From Protocol:

9.I.3. Statistical Analysis

The purpose of this analysis will be to measure the incidence of the CKD-PSIs in the study cohort and to determine the adjusted incidence rates across key factors which relate to safety in CKD. Event ascertainment will begin 4 months (with first telephone follow-up) after enrollment at which time individual events will be recorded longitudinally and cumulatively.

We will consider each specific type of event as an endpoint, but the primary analysis will be based on a composite endpoint of all CKD-PSIs endorsed for inclusion in the trial. The incidence of the events will be expressed per patient-months accrued for all participants in the study cohort and cumulative incidence rates will be determined for both the composite and individual events. Each event will be recorded per individual at the time of the event. For example, if there was an episode of hypoglycemia documented in April for a participant enrolled in January, and an exposure to NSAID in December, then that individual will have 2 CKD-PSI events per 12 patient-months.

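### Time at risk has no stated stop at dialysis or transplant, so post-ESRD months enter the pre-dialysis CKD-PSI rate and make up a larger fraction of CKD-PSI time than of non-PSI time in the hospitalization comparison

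*Combined protocol and SAP*

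**What the plan says.** All places are in the combined protocol and SAP.

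- **Population.** Justification, Objective, & Research Design, item 2, describes 350 people with Stage III to V CKD who are not yet on dialysis. The Lay Summary defines CKD the same way.
- **Primary rate.** Sample Size and Data Analysis, item 2 (protocol 9.I.3): "The incidence of the events will be expressed per patient-months accrued for all participants in the study cohort".
- **Poisson model.** Same section: the event count has a "mean being a product of the length of the follow-up period and the rate of events". The relation of entry GFR to CKD-PSI incidence is called a key analysis.
- **Hospitalization comparison.** Non-PSI time is "corresponding to the period from entry to the occurrence of the first CKD-PSI". CKD-PSI time is "corresponding to the period from the occurrence of the first CKD-PSI to last follow up time or the end of the study". A GEE with log link then gives a rate ratio. The only time-varying covariate named for it is detection of a CKD-PSI.
- **Role of ESRD.** Research Design, item 2: "Secondary outcomes: including changing renal function, hospitalization, ESRD, and death". From July 2016 the annual call records onset of ESRD treated by dialysis or transplant, through December 2021 (Lay Summary; Study Procedures, item 1).
- **Length of follow-up.** Study Procedures, item 3: participation may reach 10 years for those enrolled in 2011 and 7 years for the last enrolled in 2014. Clinic visits ended on July 1, 2016.

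**The concern.** A participant who starts dialysis or receives a transplant has left the population that the CKD-PSI rate is meant to describe. The rate's denominator and the Poisson exposure time nevertheless run on. Participants with low entry GFR can be expected to reach ESRD sooner, so the admixture is likely to be uneven across the very factor the Poisson analysis examines.

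The hospitalization comparison has a further problem. A participant moves from the non-PSI group to the CKD-PSI group at the first event and cannot move back, so CKD-PSI time is later time. ESRD also accumulates with time. If hospitalization is more frequent after ESRD, the CKD-PSI group shows a higher rate even when CKD-PSIs do nothing. That error points the same way as the study's hypothesis that CKD-PSIs contribute to adverse outcomes.

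**Working it through.** The plan gives no figure to reproduce. The check asks how much post-ESRD time the rules admit, and what that does to the rate ratio when CKD-PSIs have no effect.

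**Inputs, all assumed unless noted.** First CKD-PSI hazard λ = 0.3/yr; ESRD hazard h = 0.02, 0.05 or 0.10/yr; death μ = 0.04/yr; hospitalization rate after ESRD k = 1.5, 2 or 3 times the rate before. The three event times are independent and exponential. Follow-up T is 4 years (the clinic-visit phase allowed up to 4 annual visits) or 8 years (within the stated 7 to 10 year maxima). The documents give annual incidences of 14.8% and 30% for single CKD-PSI types and 10% to 40% in Table 4, but no ESRD, death or hospitalization rate.

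**Formulas.** Let J(a) = (1 − e^(−aT))/a.

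- All time: J(μ); before ESRD: J(h+μ).
- Non-PSI time: J(λ+μ); before ESRD: J(λ+h+μ).
- CKD-PSI time is the difference in each case.
- Post-ESRD fraction of non-PSI time: f0 = 1 − J(λ+h+μ)/J(λ+μ).
- Post-ESRD fraction of CKD-PSI time: f1 = 1 − [J(h+μ) − J(λ+h+μ)]/[J(μ) − J(λ+μ)].
- Crude rate ratio with no CKD-PSI effect: [1 + (k−1)f1]/[1 + (k−1)f0].

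**Worked case: T = 8, h = 0.05, k = 2.** J(0.34) = 2.747, J(0.39) = 2.451, J(0.04) = 6.846, J(0.09) = 5.703. Then f0 = 1 − 2.451/2.747 = 0.108. CKD-PSI time is 6.846 − 2.747 = 4.099, of which 5.703 − 2.451 = 3.252 is before ESRD, so f1 = 0.207. Ratio = 1.207/1.108 = 1.09.

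| T (yr) | h (/yr) | Post-ESRD, all time | f0 | f1 | Share of post-ESRD time in CKD-PSI group | Ratio at k = 1.5 / 2 / 3 |
|---|---|---|---|---|---|---|
| 4 | 0.02 | 3.8% | 3.0% | 4.9% | 52.5% | 1.009 / 1.018 / 1.034 |
| 4 | 0.05 | 9.1% | 7.4% | 11.7% | 52.3% | 1.021 / 1.040 / 1.075 |
| 4 | 0.10 | 17.1% | 13.9% | 21.8% | 51.9% | 1.037 / 1.069 / 1.123 |
| 8 | 0.02 | 7.2% | 4.6% | 9.0% | 74.5% | 1.021 / 1.042 / 1.080 |
| 8 | 0.05 | 16.7% | 10.8% | 20.7% | 74.1% | 1.047 / 1.089 / 1.162 |
| 8 | 0.10 | 29.7% | 19.7% | 36.4% | 73.4% | 1.076 / 1.139 / 1.239 |

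**Which group holds most post-ESRD time?** That depends on the CKD-PSI rate and the horizon. At λ = 0.3/yr the CKD-PSI group holds 32% at 2 years. In a variant with CKD-PSI recording from month 4 and no deaths, a 10% annual incidence gives 24% at 4.5 years and 35% at 7 years; a 40% incidence gives 83% to 84% at 7 years. The plan's own 14.8% and 30%, if independent, combine to 1 − 0.852 × 0.70 = 40.4% per year. If no new CKD-PSI is recorded after mid-2016, the 7-year share is 43% at 30% incidence and 55% to 56% at 40%. In every scenario f1 exceeds f0.

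**Source of the ratio.** With independent times, ESRD status at any given time since entry is unrelated to CKD-PSI status, so the ratio at that time is exactly 1. The crude excess arises because CKD-PSI time is later and time since entry is not adjusted for. Ending time at ESRD also restores 1.00 in this model, but only because the pre-ESRD hospitalization rate is held constant.

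**Effect on the CKD-PSI rate.** If the post-ESRD rate is r times the pre-ESRD rate, the pooled rate is the pre-ESRD rate times 1 + (r − 1)f, where f is the all-time fraction in the table. The documents give no basis for r, so neither the size nor the direction of this shift can be stated.

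**The case against.** **The rule may be incomplete rather than deliberate.** The wording on CKD-PSI time comes from an illustration of how one participant's second hospitalization is assigned. It does not define last follow-up or mention ESRD. The application reproduces only sections 9.I.3 and 9.I.4 of a separate protocol, so a definition could sit elsewhere. This stands: a reader might infer a considered decision to count post-ESRD time, and the documents do not show one. What they show is a time-at-risk description with no visible stop.

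**The horizon may be shorter.** A reader might take follow-up as 10 years for everyone, but that is a maximum for 2011 enrollees. After July 2016, collection narrowed to a brief annual call, and it is unclear whether those months enter the CKD-PSI denominator. This stands, and the 8-year figures are conditional on it.

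**The effect is modest.** The mid-range 4-year ratio is 1.04. Raising death after ESRD to an assumed 15%/yr lowers the 8-year 1.09 to 1.07. The 1.24 needs the highest ESRD rate, a tripled hospitalization rate and 8 years together. The calculation is of a crude ratio, not the GEE, and hospitalization is a secondary outcome. All of this stands.

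**Keeping post-ESRD time can be legitimate.** The background places ESRD downstream of CKD-PSIs. Censoring there removes part of any effect and may be informative. This stands for hospitalization, although the plan does not say that a total effect is intended. It does not justify post-ESRD months in a rate for pre-dialysis CKD.

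**Conclusion.** The point holds in limited form. The visible analysis rules neither stop nor split time at renal replacement therapy, so followed literally they put post-ESRD months into the primary CKD-PSI rate and its analysis by entry GFR. Under the assumed rates those months are 4% to 17% of person-time over 4 years and 7% to 30% over 8 years. The resulting error in the CKD-PSI rate cannot be sized from the documents.

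In the hospitalization comparison, CKD-PSI time has the higher post-ESRD fraction in every scenario examined. With no CKD-PSI effect the crude rate ratio is about 1.01 to 1.12 over 4 years and 1.02 to 1.24 over 8 years. The 8-year range applies only as far as follow-up after mid-2016 is used. All ESRD, death and hospitalization inputs are assumptions, as is independence of the event times.

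Two stronger readings are not supported. One is that most post-ESRD time necessarily falls in the CKD-PSI group; at low CKD-PSI rates or short follow-up it does not. The other is that censoring at ESRD is the only correct hospitalization analysis; it answers a different question from the total effect, and by itself leaves any trend in hospitalization before ESRD unadjusted.

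**What to change.** 1. **CKD-PSI rate and Poisson model.** End patient-months at the earliest of start of renal replacement therapy, death, last contact or end of study, and define last contact. State whether months after July 2016 count towards this rate.
2. **Hospitalization GEE.** Include time since entry as a covariate. Report the rate ratio both with time ended at renal replacement therapy and with post-ESRD time included (the total effect, if ESRD lies on the pathway). State in advance which is primary.

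The cost is small. Onset of renal replacement therapy is already collected; the team should confirm that a start date is held for each participant. The CKD-PSI rate loses some person-time and events, so its precision falls slightly. Nothing is lost for hospitalization, because both versions are reported.
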